10.5. Appendix 5: Data Display Standards & Handling Conventions

10.5.1. Reporting Process

Software	

 The SAS Version 9.4 or above will be used. 	
Reporting Area	
HARP Server	: US1SALX00259
HARP Compound	: arenv/arprod/ GSK1278863/mid205767/final_01
Analysis Datasets	

 Analysis datasets will be created according to Clinical Data Interchange Standards Consortium (CDISC) standards: Study Data Tabulation Model (SDTM) implementation guide (IG) Version 3.1.3 with some updates from Version 3.2, Analysis data model (ADaM) IG Version 1.1, and GSK ADaM specification template. For creation of ADaM datasets (ADCM/ADAE), the same version of dictionary datasets will be implemented for conversion from system independent (SI) to SDTM. 	
Generation of RTF Files	

 Rich text format (RTF) files will be generated for Tables 	

10.5.2. Reporting Standards

General	

 The current GSK Integrated Data Standards Library (IDSL) will be applied for reporting, unless otherwise stated (IDSL Standards Location: https://spope.gsk.com/sites/IDSLLibrary/SitePages/Home.aspx): 
 4.03 to 4.23: General Principles 5.01 to 5.08: Principles Related to Data Listings 6.01 to 6.11: Principles Related to Summary Tables 7.01 to 7.13: Principles Related to Graphics Do not include subject level listings in the main body of the GSK Clinical Study Report. All subject level listings should be located in the modular appendices as ICH or non-ICH listings In all displays (TFLs) the term "Subjects" will be used to refer to the "Participants". 	
Formats	
	
 GSK IDSL Statistical Principles (5.03 & 6.06.3) for decimal places (DP's) will be adopted for reporting of data based on the raw data collected, unless otherwise stated. Numeric data will be reported at the precision collected on the eCRF. The reported precision from non eCRF sources will follow the IDSL statistical principles but may be adjusted to a clinically interpretable number of DP's.
Planned and Actual Time	

 Reporting for tables, figures and formal statistical analyses: 
 Planned time relative to dosing will be used in figures, summaries, statistical analyses and calculation of any derived parameters, unless otherwise stated. The impact of any major deviation from the planned assessment times and/or scheduled visit days on the analyses and interpretation of the results will be assessed as appropriate. Reporting for Data Listings: 	

CONFIDENTIAL

205767

• Planned and actual time relative to study drug dosing will be shown in listings (Refer to IDSL Statistical Principle 5.05.1).• Unscheduled or unplanned readings will be presented within the subject's listings.	
Unscheduled Visits	

• Unscheduled visits will not be included in summary tables and/or figures.• All unscheduled visits will be included in listings.	
Descriptive Summary Statistics	
Continuous Data	Refer to IDSL Statistical Principle 6.06.1
Categorical Data	N, n, frequency, %
Graphical Displays	

• Refer to IDSL Statistical Principles 7.01 to 7.13.	
Note	

• All displays (TFL) will use the term 'Subjects' (i.e. reflect GSK Display Standards and CDISC SDTM/ADaM standards)	

10.6. Appendix 6: Derived and Transformed Data

10.6.1. General

Multiple Measurements at One Analysis Time Point

 Mean of the measurements will be calculated and used in any derivation of summary statistics but if listed, all data will be presented. If there are two values for time points other than the baseline within a time window (as per Section 10.3.1), the value closest to the target day for that window will be used. If values are the same distance from the target, then the mean will be taken.
Study Day

 Calculated as the number of days from First Dose Date: 
 Ref Date = Missing → Study Day = Missing Ref Date < First Dose Date → Study Day = Ref Date – First Dose Date Ref Date ≥ First Dose Date → Study Day = Ref Date – (First Dose Date) + 1
Screening and Washout visits

 Rescreened subject's data will only be counted once, the latest visit will only be summarized.

10.6.2. Study Population

Demographics
Body Mass Index (BMI)

 Calculated as Weight (kg) / [Height (m)]²
Extent of Exposure

 Number of days of exposure to study drug will be calculated based on the formula: The study duration will be assigned based on exposure date and by default will assign as 1 day for each date (if there is any repetition in the date we will consider only one record). Since there is no exposure end date collected for the study, we will be assigning by default value as 1 day. However, we are checking duplication in the backend. Participants who were randomized but did not report a treatment start date will be categorised as having zero days of exposure. The cumulative dose will be based on the formula: Sum of each record in incremental order on all previous records and current record value get added as cumulative. If there are any treatment breaks during the study, exposure data will be adjusted accordingly.

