7. TREATMENTS

Study treatment is defined as any investigational treatment(s), marketed product(s), placebo, or medical device(s) intended to be administered to a study participant according to the study protocol. Eligible participants will be randomized to receive **either** daprodustat or darbepoetin alfa.

Participants randomized to daprodustat will receive this study treatment daily, starting Day 1 through Day 41 (i.e., day prior to FBF & PWV procedures). Participants randomized to darbepoetin alfa will receive this study treatment every 2 weeks, starting Day 1 through Day 28.

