7.6. Treatment Compliance

Participants that are randomized to daprodustat will be instructed to return all unused study treatment at each clinic visit. A record of the number of daprodustat tablets dispensed to and returned by each participant will be maintained and reconciled with study treatment and compliance records.

Participants that are randomized to darbepoetin alfa will have supervised administration of study treatment in the clinic, with the details of each administered darbepoetin alfa dose maintained and reconciled with study treatment and compliance records.

Study treatment start and stop dates and dosing details, including dates for study treatment dose increases or reductions, will be recorded in the electronic Case Report Form (eCRF).

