6.2.5. Exposure

A listing of exposure data will be provided. This listing will include treatment, site ID, unique subject ID, dose start date, duration of time on dose, dose and dose units.

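### The SAP counts exposure as one day per dosing date on the premise that no end date is collected; the protocol and the SAP's own windows contradict that premise, and a full darbepoetin course comes out as 3 days

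*SAP*

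**What the plan says.** **SAP 10.6.2 (Extent of Exposure)** sets the rule for days: "The study duration will be assigned based on exposure date and by default will assign as 1 day for each date". Repeated dates are collapsed to one record. The reason given is "Since there is no exposure end date collected for the study, we will be assigning by default value as 1 day". Cumulative dose is a running total: "Sum of each record in incremental order on all previous records and current record value get added as cumulative". On interruptions it says only: "If there are any treatment breaks during the study, exposure data will be adjusted accordingly".

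**SAP 6.2.5** plans an exposure listing that includes "dose start date, duration of time on dose, dose and dose units". In Appendix 10 this is Listing 9. No exposure summary table is planned.

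**Protocol 7.6** says: "Study treatment start and stop dates and dosing details, including dates for study treatment dose increases or reductions, will be recorded in the" eCRF. It also requires a count of daprodustat tablets dispensed and returned, and a record of each darbepoetin dose given in clinic. Protocol 8.2 adds that the last-dose date is recorded for withdrawals.

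**SAP 10.4.1 and 10.4.2** end the on-treatment and treatment-emergent windows one day after the Study Treatment Stop Date. SAP 10.7.2.1 uses the same date to complete partial adverse event dates. SAP Table 1, which lists departures from the protocol's analysis plan, does not mention uncollected stop dates.

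**The concern.** The rule rests on a premise that the protocol contradicts and that the SAP does not hold to elsewhere. It also mixes two quantities: the number of dates on which a dose was recorded, and the time a participant spent on treatment. For a fortnightly injection these differ greatly. For a daily tablet they agree only if every tablet has its own dated record.

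The cumulative-dose rule adds record values without multiplying by days on dose. That is right when one record is one injection. It is wrong for a tablet record that stands for several days.

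At stake is the accuracy of a subject-level listing in a study with 4 completers and descriptive reporting only. SAP 2.4 defines the estimand as the effect of 6 weeks of randomized treatment, so the reported exposure should describe those weeks.

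**Working it through.** The documents state no exposure total, so there is no figure to reproduce. The check applies the SAP rule to the protocol schedule and compares the result with a start-to-stop calculation.

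**Inputs**
- Darbepoetin dosing dates: Days 1, 14 and 28 (Protocol synopsis). A further Day 42 dose is possible when the final FBF procedure is repeated (SoA footnote 18) or delayed (9.6.1.4).
- Daprodustat: "Participants randomized to daprodustat will receive this study treatment daily, starting Day 1 through Day 41" (Protocol 7).
- Daprodustat 2 mg once daily (Protocol 7.1.1.1), held constant here purely for the arithmetic.
- eCRF record structure: not in the documents, so several cases are shown.

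**Formulas**
- SAP days = number of distinct exposure dates.
- SAP cumulative dose = sum of record doses.
- Start-to-stop days = stop date − start date + 1.
- Daily-dosing cumulative dose = sum of (dose level × days at that level).

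**Darbepoetin**
- SAP rule: Days 1, 14, 28 = 3 days, or 4 days with a Day 42 dose.
- First to last injection: 28 − 1 + 1 = 28 days.
- Cumulative dose: the sum of the injections, which the SAP rule gives correctly.

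**Daprodustat, constant 2 mg, full course**

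Start to stop: 41 − 1 + 1 = 41 days; 41 × 2 mg = 82 mg.

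| Assumed records | SAP days | SAP cumulative dose |
|---|---|---|
| One per daily dose | 41 | 41 × 2 = 82 mg |
| Days 1, 14 and 28 | 3 | 3 × 2 = 6 mg |
| Days 1 and 28 | 2 | 2 × 2 = 4 mg |
| Day 1 only | 1 | 1 × 2 = 2 mg |

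One and the same course can therefore be derived as anything from 1 to 41 days and from 2 to 82 mg.

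**The premise**
- If a stop date exists, as Protocol 7.6 requires and SAP 10.4.1, 10.4.2 and 10.7.2.1 assume, the one-day default is not needed for duration.
- If it does not exist, the stop date behind those three sections has no stated source. The missing-date rules in 10.4.1 and 10.4.2 would then class assessments and adverse events as on-treatment by default, including those at the follow-up visit.
- Either way, one of the statements has to change.

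**The case against.** The strongest reply is that the SAP wording fits one record per dosing date. On that reading the daprodustat values are correct, and 3 is a correct count of darbepoetin dosing days that needs only a proper label. The SAP may also mean that individual exposure records have no end-date field, while an overall stop date exists. The effect is small: there is no exposure table, no planned comparison of exposure between arms, and no pharmacodynamic summary that uses the derived duration. Cumulative dose is not among the items that SAP 6.2.5 names for the listing.

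Much of this stands. A reader might infer three stronger things that the documents do not support:
- **That daprodustat exposure is understated about 13.7-fold (82/6).** This holds only for records on Days 1, 14 and 28, which is an assumption.
- **That exposure is the only evidence of a completed course, or that a full course cannot be told from an interrupted one.** Table 1.1 and Listings 2 and 3 show disposition, withdrawal and treatment discontinuation. Under Protocol 8.1, participants who stop treatment are withdrawn. Listing 9 shows dose start dates, so darbepoetin injections stay visible.
- **That darbepoetin exposure should be credited with 14 days after the last injection.** No section says so. With a Day 42 dose that convention gives 42 + 14 − 1 = 55 days, although a repeat FBF procedure takes place at most one week later.

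The reply does not rescue the rule. The SAP does not state the record structure on which the daprodustat result depends. A count of injections remains a wrong entry under a time-on-dose label. If only the per-record end date is missing, the overall stop date is available and should be used. The clause on treatment breaks gives no method.

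**Conclusion.** The derivation is wrong as written, with limited impact. The firm result is darbepoetin: 3 days under the rule against 28 from first to last injection. It assumes a dated record for each injection and a stop date equal to the last injection. Expressing coverage to the end of the 42-day treatment period would need a convention that the documents do not give.

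For daprodustat the finding is conditional. The rule gives the correct 41 days and 82 mg with daily records, and understates both with fewer records. The contradiction over whether stop dates are collected stands on the text alone and needs no assumption.

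The consequence is confined to Listing 9 and any derived cumulative dose. The primary and secondary pharmacodynamic summaries are not affected.

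**What to change.** Rewrite the exposure derivation in SAP 10.6.2:
- **Duration:** treatment stop date − start date + 1, minus documented breaks, from the dates that Protocol 7.6 requires. State how a break is identified and subtracted.
- **Daprodustat cumulative dose:** sum of dose level × days at that level, checked against tablets dispensed and returned.
- **Darbepoetin:** show the number of injections and the total dose (sum of records). Label any count of dates as dosing days, not as duration of exposure.
- **Premise:** delete the statement that no end date is collected. If stop dates were in fact not collected, enter this in SAP Table 1 as a departure from the protocol, use last-dose, visit and tablet-count data instead, and state what defines the Study Treatment Stop Date in 10.4.1, 10.4.2 and 10.7.2.1.

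If the dates were collected, the cost is SAP wording and one derived-dataset change. If they were not, reconstructing dates from visit and tablet-count data takes somewhat more work, though for few participants.

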10.6.3. Safety

Laboratory Parameters

 If a laboratory value which is expected to have a numeric value for summary purposes, has a non-detectable level reported in the database, where the numeric value is missing, but typically a character value starting with '<x' or '>x' (or indicated as less than x or greater than x in the comment field) is present, the number of significant digits in the observed values will be used to determine how much to add or subtract in order to impute the corresponding numeric value. 
 Example 1: 2 Significant Digits = '<x' becomes x – 0.01 Example 2: 1 Significant Digit = '>x' becomes x + 0.1 Example 3: 0 Significant Digits = '<x' becomes x – 1

CONFIDENTIAL

205767

Laboratory Parameters

 • If a laboratory value which is expected to have a numeric value for summary purposes, has a non-detectable level reported in the database, where the numeric value is missing, but typically a character value starting with '\leqx' or '\geqx' is present, then the corresponding numeric value will be set equal to x.

 • If there is more than one laboratory value on the same date for the same laboratory test, then the laboratory values associated with scheduled visits will be used.

 • The following will be used to convert laboratory values from SI units to conventional units if the specific lab value is not already in this format. [Iverson, 2007]: 
 • Hemoglobin and MCHC: Divide the g/L value by 10 to get the g/dL value. • TSAT: If unit is not percentage then multiply with 100 to get the % value. • Lab values that are converted will be reported in place of original value

 • Heart rate and pulse rate can be used interchangeably • Total calcium and calcium can be used interchangeably • Total protein and protein can be used interchangeably • Total bilirubin and bilirubin can be used interchangeably • TSAT and transferrin saturation can be used interchangeably • Folate and Vitamin B9 can be used interchangeably

 • Baseline HGB will be based either on the pre-dose value on Day 1 or screening value. Any unscheduled HGB values taken after the pre-dose value on Day 1 will not be used.

 • Scheduled central laboratory HGB values and HemoCue HGB value will be used for report. Conversion values (g/L value g/dL) also will be reported.
PCI Criteria Categories

 • PCI criteria categories are: To Low, To w/in Range or No Change, To High • Subjects with a missing baseline value are to be assumed to have a normal/within range baseline value.

10.6.4. Pharmacodynamic

Primary/Principle Secondary/Secondary/Exploratory Endpoints
FBF Ratio/Absolute FBF

 • If either a Day 1 Repeat or Day 42 Repeat measurement is available for forearm blood flow, the repeat value will be used instead. • Forearm blood flow for a given challenge agent dose (infused arm), or for values from the non-infused arm, will be the mean of 5 continuous time point values. • Forearm blood flow ratio is defined as the ratio of a subject's treatment (infused) arm value divided by the non-treatment (non-infused) arm value 
 ○ First, the mean of both the infused and non-infused arm will be taken separately for the given five measurements before going into the ratio calculation. An example of this is shown in the table below:

CONFIDENTIAL

205767

Primary/Principle Secondary/Secondary/Exploratory Endpoints			
	Infused	Non-Infused	
Measurement 1	1.2	1.01	
Measurement 2	1.1	1	
Measurement 3	1.4	1.2	
Measurement 4	1.5	1.1	
Measurement 5	1.6	1.3	FBF Ratio
Average	1.36	1.122	1.212121212

- Absolute forearm blood flow is defined as the infused arm value.

Secondary Endpoint
PWV Dataset
For the PWV dataset, there are two recorded values for each variable per day, with the option to collect a third value if the first two values varied (Refer: SRM) too much from each other. The average of the two closest absolute values will be used for analysis purposes.

10.7. Appendix 7: Reporting Standards for Missing Data

10.7.1. Premature Withdrawals

Element	Reporting Detail
General	
 Participant study completion (i.e. as specified in the protocol) was defined as a participant who has completed all phases of the study including the last visit or the last scheduled procedure Withdrawn subjects were not replaced in the study. All available data from participants who were withdrawn from the study will be listed and all available planned data will be included in summary tables and figures, unless otherwise specified. Withdrawal visits will be slotted as per Appendix 3: Assessment Windows or will be summarised as withdrawal visits.

10.7.2. Handling of Missing Data

Element	Reporting Detail
General	
 Missing data occurs when any requested data is not provided, leading to blank fields on the collection instrument: 
 These data will be indicated by the use of a “blank” in subject listing displays. Unless all data for a specific visit are missing in which case the data is excluded from the table. Answers such as “Not applicable” and “Not evaluable” are not considered to be missing data and should be displayed as such.
Outliers	
 Any participants excluded from the summaries and/or statistical analyses will be documented along with the reason for exclusion in the clinical study report.

10.7.2.1. Handling of Missing and Partial Dates

Element	Reporting Detail
General	
 Partial dates will be displayed as captured in subject listing displays.
Adverse Events	
 The eCRF allows for the possibility of partial dates (i.e., only month and year) to be recorded for AE start and end dates; that is, the day of the month may be missing. In such a case, the following conventions will be applied for calculating the time to onset and the duration of the event: 
 Missing Start Day: First of the month will be used unless this is before the start date of study treatment; in this case the study treatment start date will be used and hence the event is considered On-treatment as per Appendix 4: Study Phases and Treatment Emergent Adverse Events. Missing Stop Day: Last day of the month will be used, unless this is after the stop date of study treatment; in this case the study treatment stop date will be used. Missing Start Month: ‘January’ will be used unless this makes the start date before the month of start of study treatment; in this case the month of study treatment start will be used. Missing Stop Month: ‘December’ will be used, unless this is after the stop date of study treatment; in this case the study treatment stop date will be used.

CONFIDENTIAL

205767

Element	Reporting Detail
	
• Completely missing start or end dates will remain missing, with no imputation applied. Consequently, time to onset and duration of such events will be missing.
Concomitant Medications/Medical History	
• Partial dates for any concomitant medications recorded in the CRF will be imputed using the following convention:
◦ If the partial date is a start date, a '01' will be used for the day and 'Jan' will be used for the month◦ If the partial date is a stop date, a '28/29/30/31' will be used for the day (dependent on the month and year) and 'Dec' will be used for the month.• The recorded partial date will be displayed in listings.

CONFIDENTIAL

205767

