9.2.1. Time Period and Frequency for Collecting AE and SAE Information

- Any SAEs assessed as related to study procedure (e.g., protocol-mandated procedures, invasive tests, or change in existing therapy) or related to a GSK product will be recorded in the eCRF from the time a participant consents to participate in the study up to and including any follow-up contact.
- AEs and SAEs will be collected from randomization (Day 1) until the follow-up visit at the time points specified in the SoA (See Section [2](#)).
- Medical occurrences that begin before the start of study treatment but after obtaining informed consent will be recorded on the Medical History/Current Medical Conditions section of the eCRF and not the AE section.
- All SAEs will be recorded and reported to the sponsor or designee immediately and under no circumstance should this exceed 24 h, as indicated in [Appendix 4](#). The investigator will submit any updated SAE data to the sponsor within 24 h of it being available.
- Investigators are not obligated to actively seek AEs or SAEs in former study participants. However, if the investigator learns of any SAE, including a death, at any time after a participant has been discharged from the study, and he/she considers the event to be reasonably related to the study treatment or study participation, the investigator must promptly notify the sponsor.
- The method of recording, evaluating, and assessing causality of AEs and SAEs and the procedures for completing and transmitting SAE reports are provided in [Appendix 4](#).

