9.6.1.2. Participants Unable to Complete FBF Procedure

If a participant is unable to complete the Day 1 FBF procedure with all three doses of the ACh infusion and there is reasonable expectation a second attempt will be successful, one additional attempt may be made in a subsequent visit up to 1 week later, if the participant agrees. In this case, the participant should not be dosed with study drug until after the FBF procedures are completed at the repeat visit.

If participants are unable to complete the Day 42 FBF procedure with all three doses of the ACh infusion, one additional attempt may be made in a subsequent visit up to 1 week later, if the participant agrees. For participants that will have repeat FBF procedures performed, details can be found in Section 9.6.1.4.

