10.4. Appendix 4: Study Phases and Treatment Emergent Adverse Events

10.4.1. Study Phases

Assessments and events will be classified according to the time of occurrence relative to study treatment start and stop dates.

Study Phase	Definition
Pre-Treatment	Date < Study Treatment Start Date
On-Treatment	Study Treatment Start Date ≤ Date ≤ Study Treatment Stop Date + 1 day
Post-Treatment	Date > Study Treatment Stop Date + 1 day

- If the treatment stop date is missing and the treatment start date is non-missing, then the assessment will be considered On-Treatment.

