10.4.2. Treatment Emergent Flag for Adverse Events

Flag	Definition
Treatment Emergent	
 • If AE onset date is on or after treatment start date & on or before treatment stop date + 1 day • Study Treatment Start Date ≤ AE Start Date ≤ Study Treatment Stop Date + 1 day

NOTES:

- If the study treatment stop date is missing, then the AE will be considered to be On-Treatment.
- Time of study treatment dosing and start/stop time of AEs should be considered, if collected.

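### The SAP's missing-day rule gives an adverse event whose recorded month wholly precedes dosing a Day 1 onset and an on-treatment flag

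*SAP*

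**What the plan says.** SAP 10.7.2.1 describes partial AE dates as having month and year, where "the day of the month may be missing". For a missing start day the rule is: "First of the month will be used unless this is before the start date of study treatment; in this case the study treatment start date" and it continues "will be used and hence the event is considered On-treatment as per Appendix 4". For a missing start month, January is used "unless this makes the start date before the month of start of study treatment", in which case the month of first dose replaces it.

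SAP 10.4.2 defines the treatment-emergent flag as "Study Treatment Start Date ≤ AE Start Date ≤ Study Treatment Stop Date + 1 day". SAP 10.4.1 defines the pre-treatment phase as "Date < Study Treatment Start Date".

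Three protocol provisions decide whether pre-dose events can reach this rule:

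- Section 9.2.1 says that serious adverse events (SAEs) related to a study procedure or a sponsor product "will be recorded in the eCRF from the time a participant consents to participate in the study". The same section collects AEs from randomization on Day 1, but sends occurrences that begin after consent and before treatment to the medical history page.
- Section 9.6.1.2 allows a failed Day 1 forearm blood flow (FBF) procedure to be repeated: "one additional attempt may be made in a subsequent visit up to 1 week later". Dosing waits for that repeat.
- The Schedule of Activities includes an AE assessment at Repeat Day 1.

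**The concern.** Moving an uncertain onset to the first dose is a sound conservative choice when the recorded month is the month of first dose, because the order of event and dose is then unknown. When the recorded month is earlier, the order is known. The rule overrides that information and contradicts the SAP's own definition of the pre-treatment phase.

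At stake are the derived time to onset and duration, and the on-treatment or treatment-emergent status, of any pre-dose event entered on the AE page without a day. A complication of the Day 1 arterial procedure that preceded a delayed first dose is the kind of event that could be affected.

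**Working it through.** The plan gives no figure on this point, so there is none to reproduce. The check has three parts.

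**1. The rule applied literally.** Illustrative assumption: first dose on 15 March 2019, last dose on Day 41. The amended rule substitutes the treatment start date only if the recorded month and year match it.

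| Recorded onset | Onset under SAP rule | Flag | Onset under amended rule | Flag |
|---|---|---|---|---|
| Jan 2019 | 15 Mar 2019 | emergent | 1 Jan 2019 | not emergent |
| Feb 2019 | 15 Mar 2019 | emergent | 1 Feb 2019 | not emergent |
| Mar 2019 | 15 Mar 2019 | emergent | 15 Mar 2019 | emergent |
| Apr 2019 | 1 Apr 2019 | emergent | 1 Apr 2019 | emergent |

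The January and February rows are wrong under the SAP rule. The March and April rows do not change. With screening up to 30 days before Day 1 and a repeat up to 7 days later, 37 days before 15 March is 6 February. So February is reachable under the protocol's timing; January is there only to show how the rule behaves.

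**2. Which records can reach the rule.** Setting the Protocol 9.2.1 provisions side by side leaves three routes:

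- related SAEs, which are collected from consent;
- events between Day 1 and a first dose delayed by a Repeat Day 1, where 9.2.1 pulls both ways (AEs are collected from randomization, but occurrences before treatment go to medical history);
- pre-dose events entered on the AE page by mistake.

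**3. How often the calendar month differs, given such a record.** An onset k days before first dose falls in an earlier month when the day-of-month of first dose is at most k. In a 365-day year that holds for 12k start dates when k is 28 or less, for 28 + 11 × 29 = 347 when k = 29, and for 28 + 11 × 30 = 358 when k = 30.

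- Onsets spread evenly over 1 to 7 days: 12 × (1 + … + 7) / (7 × 365) = 336 / 2,555 = 13.2%.
- Onsets spread evenly over 1 to 30 days: (12 × 406 + 347 + 358) / (30 × 365) = 5,577 / 10,950 = 50.9%, where 406 = 1 + … + 28.

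A different question is how many start dates have a window that reaches an earlier month at all. That is 12 × 7 = 84 of 365 (23%) for 7 days and 358 of 365 (98%) for 30 days.

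**Missing month.** This rule replaces the month and does not expressly change the year. If the recorded year is the year of first dose, the result is acceptable because the order is unknown. If the recorded year is earlier, the rule inserts the first-dose month in that earlier year. The missing-day rule then moves the onset to the treatment start date. The error therefore needs an earlier recorded year and the day rule applied afterwards.

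**The case against.** The strongest case against is that almost nothing passes through this gap, and that little depends on what does.

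- **Routing.** The medical history provision in Protocol 9.2.1 is tied to the start of treatment, so it can be read as covering the Repeat Day 1 gap too. This stands as a limit on exposure. It does not remove related SAEs.
- **Missing days will be rare.** SAEs must be reported within 24 hours, and a complication of the FBF procedure is tied to a dated visit. This stands.
- **Outputs.** The safety tables in SAP 10.10.5 cover laboratory, ECG and vital-sign data only. AEs appear only in Listings 10 to 12, and SAP 10.7.2.1 shows partial dates there as captured, so the recorded month stays visible. This stands.
- **Scope of the rule.** The lead-in in SAP 10.7.2.1 says the conventions serve time to onset and duration. This does not rescue the rule, because the missing-day bullet itself carries the imputed date into on-treatment status.

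A reader might infer that procedural complications would be attributed to daprodustat or darbepoetin alfa. The documents do not support that. The flag is a timing label, and Protocol Appendix 4 has the investigator assess causality for each event. Nor does the concern extend to an arterial procedure at screening: the Schedule of Activities has only brachial artery palpation there, and the first FBF procedure is on Day 1.

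**Conclusion.** The rule is wrong as written for recorded months that wholly precede the first-dose month. No other SAP provision exempts such events. The consequence is limited to an incorrect derived onset time, and with it duration, and an incorrect on-treatment or treatment-emergent flag. No planned summary table changes.

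The 13% and 51% assume onsets spread evenly over the 7 or 30 days before dosing and start dates spread evenly over the year. A reader might take them as expected misclassification rates, but they apply only once a pre-dose event is on the AE page with its day missing. The documents give no basis for estimating how often that happens. SAP Table 1 (Section 2.1) reports only 4 completed subjects, so each event can be read individually in the listings. This is a minor point, worth correcting because the correction is simple.

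**What to change.** Reword the missing-day rule in SAP 10.7.2.1 along these lines: *If the recorded month and year equal those of first dose, use the treatment start date; otherwise use the first of the recorded month.* Earlier months then stay pre-treatment, and the conservative choice remains wherever the order is truly unknown.

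Reword the missing-month rule to match: *Use the first-dose month only if the recorded year equals the year of first dose; otherwise use January.*

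The cost is two lines of SAP text and one programming condition. No data collection or planned display changes.
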